7.3. Exclusion Criteria

The presence of any of the following will exclude a subject from enrollment:

- 1. Any significant medical condition, laboratory abnormality, or psychiatric illness that would prevent the subject from participating in the study.
- 2. Other causes of neuropathy in diabetic subjects: chronic inflammatory demyelinating polyneuropathy; neuropathy due to vitamin B12 deficiency, hypothyroidism, and uremia syndrome; and neuropathy due to entrapment or trauma.

- 3. A reversible course of acute painful diabetic neuropathy syndrome: treatment-induced diabetic neuropathy that presents in the setting of rapid glycemic control; diabetic neuropathic cachexia; and diabetic anorexia, a diabetic neuropathy that is seen with intentional weight loss.
- 4. History of a prior diagnosis of severe peripheral arterial disease (PAD).
- 5. Thrombocytopenia and coagulopathy, to avoid severe bruising or bleeding due to multiple intramuscular (IM) injections.
- 6. Any condition including the presence of laboratory abnormalities that places the subject at unacceptable risk if he or she were to participate in the study.
- 7. Any condition that confounds the ability to interpret data from the study.
- 8. Subjects who are taking opioids for the treatment of DPN.
- 9. Pregnant or lactating females.
- 10. Subjects with a body mass index $> 40 \text{ kg/m}^2$ at screening.
- 11. Neuropathy resulting from a condition other than DM and/or significant co-morbid neurological diseases (eg, Parkinson's disease, epilepsy, multiple sclerosis, alcoholic peripheral neuropathy), or exposure to agents suspected to cause symptoms of neuropathy (such as but not limited to metronidazole, antituberculosis medications, and heavy metals).
- 12. Advanced neuropathy as measured by the absence of sural sensory nerve action potential, or a UENS>24 and or a NIS-LL>10.
- 13. History of a prior diagnosis of Critical Limb Ischemia.
- 14. History of diabetic foot ulceration (at any time) and/or or undergoing a limb revascularization procedure(s) and/or amputation(s) due to DM.
- 15. Diagnosis of Type 1 DM and/or any of the following: diagnosis of DM prior to age 35 years; insulin required to treat DM within 1 year after DM diagnosis; history of diabetic ketoacidosis.
- 16. AST, ALT, or alkaline phosphatase ≥ 2.5 x the upper limit of normal (ULN) at screening.
- 17. Estimated glomerular filtration rate (eGFR) < 30 mL/min/1.73 m² at Screening calculated using the Modification of Diet in Renal Disease Study equation (Levey, 2006) or history of an abnormal eGFR < 60 and decline > 15 mL/min/1.73 m² below normal in the past year.
- 18. Bilirubin level > 2 mg/dL (unless subject has known Gilbert's disease) at screening.
- 19. Untreated chronic infection or treatment of any infection with systemic antibiotics within 4 weeks prior to dosing with IP.
- 20. Uncontrolled hypertension (defined as diastolic blood pressure > 100 mmHg or systolic blood pressure > 180 mmHg during screening at 2 independent measurements taken while subject is sitting and resting for at least 5 minutes).

- 21. History of significant cardiac disorders including but not limited to malignant ventricular arrhythmia, CCS Class III-IV angina pectoris, myocardial infarction/ percutaneous coronary intervention (PCI) / coronary artery bypass graft (CABG) in the 6 months prior to signing the informed consent ICF, pending coronary revascularization in the following 3 months, transient ischemic attack/cerebrovascular accident in the 6 months prior to signing the informed consent form, and/or New York Heart Association [NYHA] Stage III or IV congestive heart failure (Appendix C). Note: Stable Canadian Cardiovascular Society (CCS) Class I-II angina is allowed (Appendix D).
- 22. Poorly controlled DM (hemoglobin A1c > 10%) at screening.
- 23. Untreated proliferative retinopathy at screening.
- 24. Life expectancy less than 2 years due to concomitant illnesses.
- 25. History of malignancy within 5 years except for the following circumstances: basal cell or squamous cell carcinoma of the skin, remote history of cancer now considered cured or positive Pap smear with subsequent negative follow-up.
- 26. History of hypersensitivity to any of the components of the product formulation (including bovine or porcine products, dextran 40, and dimethyl sulfoxide [DMSO]).
- 27. Subject has received an investigational agent —an agent or device not approved by the US Food and Drug Administration (FDA) for marketed use in any indication— within 90 days (or 5 half-lives, whichever is longer) prior to treatment with study therapy or planned participation in another therapeutic study prior to the completion of this study or has received previous gene or cell therapy at any time.

8. DESCRIPTION OF STUDY TREATMENTS

8.1. Description of Investigational Product

PDA-002 is characterized as a cellular angiogenic and immune modulating agent with therapeutic potential. The product contains a mesenchymal-like cell population derived from normal, full-term human placental tissue. The cells are culture-expanded as a plastic-adherent, undifferentiated in vitro cell population that expresses the nominal phenotype CD34-, CD10+, CD105+, and CD200+. The cells constitutively express moderate levels of HLA Class I and undetectable levels of HLA Class II.

These cells demonstrate a range of potential biological activities which include the ability to (1) induce endothelial cell survival, migration and tube formation, showing angiogenic and cytoprotective potential, and (2) modulate T-cell repertoire and affect the M1/M2 balance of macrophages demonstrating an immune modulatory effect. Based on these properties, the proposed study will evaluate the safety of PDA-002 in subjects with DPN.

PDA-002 or placebo (vehicle control) units will be shipped to the study sites as cryopreserved units and will be thawed and filled into syringes prior to IM injection. A PDA-002 unit are supplied at 2 dosage strengths and contains approximately 3 or 30 million cells in 4.5 mL of a 5.75% dextran 40/10% human serum albumin (HSA) solution containing 2.5% DMSO for cryopreservation. The solution also contains Plasma-Lyte and saline to maintain the cells' osmotic environment. Placebo (vehicle control) units contain the above-mentioned components, without any cells. The product is intended for allogeneic use.

8.2. Treatment Administration and Schedule

Investigational product (IP) will be administered on Study Days 1, 29 and 57. Thawing of the IP should not begin until it is confirmed that the subject meets the inclusion/exclusion criteria. Investigational product thawing will be performed by qualified site personnel according to the instructions in Appendix E. Three 3 mL syringes will each be filled with 1.5 mL of IP, and then capped. Syringes will be masked to preserve blinding, and transferred to the personnel administering the injections.

Subjects will receive IP administered as fifteen 0.30 mL injections (approximately 4.5 mL total) in one leg. The target region is suggested to be below the knee and above the ankle. Injections are suggested to be at least 1 cm apart horizontally and laterally and at a depth of approximately 1 to 4 cm. It is suggested that they be administered in a pattern of 3 x 5 injections around the leg, and injections should not be near a blood vessel. The administrator will be blinded to treatment.

PDA-002 is not intended for intravenous administration. When the injection is given, the syringe should be aspirated to avoid inadvertent venous administration. If any blood is aspirated into the syringe, the needle is to be pulled out a little, and the syringe re-aspirated. If no blood is seen, the IP may be injected.

Vital signs (including heart rate, respiration, blood pressure, body temperature) will be monitored prior to starting the injections and at 1 and 2 hours (\pm 15 minutes) after completion of

the injections. Blood samples for tryptase and histamine, coagulation assessments, and exploratory biomarkers will be collected as indicated in the Table of Events (Table 1).

The investigational centers must also offer appropriate supplemental services that support clinical care to ensure that the protocol specified IP administration and monitoring will be followed.

Administration Instructions. Under aseptic conditions, PDA-002 or placebo will be injected IM at 15 sites in one limb on Study Days 1, 29, and 57. The injection volume will be 0.30 mL per injection site. A 3.0 mL syringe with a 20 to 22-gauge 1.5-inch long needle will be used to inject the IP. The target region is suggested to be below the knee and above the ankle. Injections are suggested to be at least 1 cm apart horizontally and laterally and at a depth of approximately 1 to 4 cm. It is suggested that they be administered in a pattern of 3 x 5 injections around the leg, and injections should not be near a blood vessel. The administrator and the subject will be blinded to treatment.

A diagram of the recommended injection grid and anatomical site selection is provided in Appendix E.

The entire thawed IP must be administered within 4 hours of thaw start time and within 1 hour of the syringe fill time. In the event that it becomes medically necessary to stop the injections, the stop time of the injections as well as the time the injections are resumed must be noted in the eCRF and in the source documents. If less than the total injection volume is administered, the volume injected should be recorded and the sponsor should be notified.

Note: For this study, all \geq Grade 3 allergic reactions associated with the use of IP must be reported to Celgene Cellular Therapeutics as an SAE within 24 hours of the investigator's knowledge of the event.

8.2.1. Discontinuation

The reason for discontinuation should be recorded in the eCRF and in the source documents. The decision to discontinue a subject remains the responsibility of the treating physician, which will not be delayed or refused by the sponsor. However, prior to discontinuing a subject, the investigator may contact the Medical Monitor and forward appropriate supporting documents for review and discussion. Of note, the investigator is not required to contact a medical monitor to discuss discontinuation or unblinding as the investigator has the ability to discontinue or rapidly unblind subjects.

Subjects who discontinue will have the procedures performed as listed in the Early Termination column as per the Table of Events (Table 1).

8.2.2. Overdose

An overdose is defined for this protocol as a subject receiving any dose of greater than 30×10^6 cells in a 24 hour period. Adverse events associated with an overdose must be collected as an Adverse Event as outlined in Section 11.2. Evaluation of Adverse Events.

Eligible subjects will be randomized to one of 3 treatment arms (3×10^6 PDA-002 cells, 30×10^6 PDA-002 cells, or placebo) via Interactive Voice Response System (IVRS) across sites in a double-blind fashion.

8.3. Method of Treatment Assignment

Eligible subjects will be randomized to one of 3 treatment arms (3×10^6 PDA-002 cells, 30×10^6 PDA-002 cells, or placebo) via Interactive Voice Response System (IVRS) across sites in a double-blind fashion.

The unblinded pharmacist/designee at the study site will prepare the appropriate IP and deliver it to the personnel performing the injections. All other site staff, including the principal investigator and research coordinator and sponsor will remain blinded to study treatment assignment.

Pharmacists should consult the pharmacy manual for detailed instructions on the preparation and handling of PDA-002 for this study.

8.4. Packaging and Labeling

Each vial of IP supplied by the sponsor will bear Celgene Cellular Therapeutics' name and address, study product name and descriptor, and traceable lot number. Additional product information including the date of manufacture, the volume of product contained within the vial, and cell concentration (for active cells) will also be noted. Finally, the label will contain the standard caution statement for investigational products.

The syringe rack label, affixed subsequently to thawing/dilution and prior to administration, will provide expiry, volume, and handling instructions.

The label(s) for IP will include sponsor name, address and telephone number, the protocol number, IP name, dosage form and strength (where applicable), amount of IP per container, lot number, expiry date (where applicable), medication identification/kit number, dosing instructions, storage conditions, and required caution statements and/or regulatory statements as applicable. Additional information may be included on the label as applicable per local regulations.

8.5. Investigational Product Accountability and Disposal

Celgene (or designee) will review with the investigator and relevant site personnel the process for IP return, disposal, and/or destruction including responsibilities for the site versus Celgene (or designee).

The investigator(s) or designee is responsible for taking an inventory and performing a visual inspection of each shipment of items received and for completing the "Human Placenta-Derived Cells (PDA-002) Product Receipt Record" enclosed within the envelope provided with the shipment. The investigator(s) or designee will verify the accuracy of the information on the form, sign and date it, retain a copy in the study file, and return a copy to the sponsor.

At the study site, all investigational IP will be stored in a locked, safe area to prevent unauthorized access. The IP should remain in the cryogenic shipper provided by Celgene until time of use.

Accurate recording of all IP administration (including dispensing and dosing) will be made in the appropriate section of the subject's eCRF and in the source documents.

The investigator(s) or designee(s) is responsible for accounting for all IP that is issued to the investigative site during the course of the study.

If any IP is lost or damaged, its disposition should be documented in the source documents. The sponsor will provide instructions to the investigator(s) for the return or destruction of unused IP and IP supplies at the end of the study.

PDA-002 is regulated by the US FDA as a human cellular product. The FDA (21 Code of Federal Regulations [CFR] 1271.290) requires that a record-keeping system be used to track human cellular and tissue-based products from the donor to the consignee and vice versa, or any other final disposition (for example, shipment was lost or the integrity of the unit was compromised). In accordance with this regulation, Celgene Cellular Therapeutics (CCT) has established a tracking system for PDA-002.

For each unit of PDA-002 that is administered, it is important to maintain records sufficient to permit prompt identification of the recipient. At no time will the identification of the donor be known by the subjects in the clinical study.

To facilitate an effective tracking process:

- Affix the PDA-002 tracking labels provided with the units to the recipient's medical records and/or other pertinent records, if any, for each unit of PDA-002 that is administered to a subject.
- Maintain the records described above and any other records necessary to permit prompt tracking of each unit of PDA-002 to its recipient or other final disposition.
- Ensure all such records are legible, accurate, indelible, and secure.
- Ensure all such records are readily available and allow the sponsor and any authorized government officers prompt access to such records to the extent required by law.
- Ensure that the record security systems are adequate to ensure the confidentiality of recipients who were administered PDA-002.
- Retain the records referenced in this document for at least 10 years after the date of the administration of PDA-002 to the recipient or, if that date is not known, the date the product is received or disposed, whichever is latest.
- Do not further distribute PDA-002.

Celgene will instruct the investigator on the return, disposal, and/or destruction of investigational product and/or medical device materials if applicable.

Celgene (or designee) will review with the investigator and relevant site personnel the process for IP return, disposal, and/or destruction including responsibilities for the site versus Celgene (or designee).

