16.1. Study Monitoring and Source Data Verification

Celgene ensures that appropriate monitoring procedures are performed before, during and after the study. All aspects of the study are reviewed with the Investigator and the staff at a study initiation visit and/or at an investigator meeting. Prior to enrolling subjects into the study, a Celgene representative will review the protocol, eCRFs, procedures for obtaining informed consent, record keeping, and reporting of AEs/SAEs with the Investigator. Monitoring will include on-site visits with the Investigator and his/her staff as well as any appropriate communications by mail, email, fax, or telephone. During monitoring visits, the facilities, investigational product storage area, eCRFs, subject's source documents, and all other study documentation will be inspected/reviewed by the Celgene representative in accordance with the Study Monitoring Plan.

Accuracy will be checked by performing source data verification that is a direct comparison of the entries made into the eCRFs against the appropriate source documentation. Any resulting discrepancies will be reviewed with the Investigator and/or his/her staff. Any necessary corrections will be made directly to the eCRFs or via queries by the Investigator and/or his/her staff. Monitoring procedures require that informed consents, adherence to inclusion/exclusion criteria and documentation of SAEs and their proper recording be verified. Additional monitoring activities may be outlined in a study-specific monitoring plan.

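### Section 8.5 lets sites file PDA-002 tracking labels in medical records, and lets a blinded investigator inspect shipments, without saying how the blind in 8.3 and 8.7 is kept

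*Combined protocol and SAP*

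**What the plan says.** **Who is blinded.** Section 8.3 has an unblinded pharmacist or designee prepare the product, and then states: "All other site staff, including the principal investigator and research coordinator and sponsor will remain blinded to study treatment assignment". Section 8.7 keeps site personnel and subjects blinded throughout, and sponsor personnel and their designees blinded until the Month 6 database lock, with listed exceptions. Those exceptions are the supply group that ships product, drug safety, one biomarker scientist, the site pharmacist or designee, the IVRS group and the DMC. Investigators and monitors are not among them.

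**Tracking labels.** Section 8.5 reads "Affix the PDA-002 tracking labels provided with the units to the recipient's medical records" and the same sentence continues "and/or other pertinent records, if any, for each unit of PDA-002 that is administered to a subject". It then asks that these records be easy to retrieve and promptly open to the sponsor. The one protection it states is recipient confidentiality.

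**What a PDA-002 unit is.** Section 8.1: "A PDA-002 unit are supplied at 2 dosage strengths and contains approximately 3 or 30 million cells". Placebo is described apart: "Placebo (vehicle control) units contain the above-mentioned components, without any cells".

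**Receipt of shipments.** Section 8.5: "The investigator(s) or designee is responsible for taking an inventory and performing a visual inspection of each shipment of items received". The same person signs a receipt record, files a copy in the study file and returns one to the sponsor. On vial labels, section 8.4 says that "the volume of product contained within the vial, and cell concentration (for active cells) will also be noted".

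**Who reads the records.** Under section 16.1, at monitoring visits "the facilities, investigational product storage area, eCRFs, subject's source documents, and all other study documentation will be inspected/reviewed by the Celgene representative". Section 14.2 gives monitors direct access to medical records.

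**The concern.** The tracking instruction is written for PDA-002 units. If it means what section 8.1 means by that term, an active subject's chart may carry a tracking label and a placebo subject's chart has no reason to. The people who score neurological signs, grade adverse events and judge their relationship to treatment are meant to be blinded, and the chart is ordinary source material for them and for the monitor. A site could therefore disclose allocation while following the protocol exactly, so no deviation would be recorded.

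Shipment inspection is a second route that does not depend on the tracking label. The rule names the investigator first and does not confine the task to unblinded staff, although active vials state a cell concentration.

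At stake are the examiner-scored exploratory scales (UENS, NIS-LL) and the severity and causality components of the secondary safety endpoint in section 3.2. With 8 subjects per arm, a few revealed allocations would matter.

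**Working it through.** No figure in the plan bears on this point, so the check is a comparison of sections, followed by a count of units.

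1. **Does the label rule cover placebo?** Section 8.5 speaks of IP when it deals with general accountability. It changes to PDA-002 where it invokes the federal tracking rule for human cellular products and tracing between donor and recipient. Section 8.1 gives PDA-002 units cells and placebo units none. The literal reading is active units only. No tracking label for placebo is described anywhere.

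2. **Where may the label go?** The medical record, another pertinent record, or both. A pharmacy log would comply, and so would the chart. Nothing steers the site to the log.

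3. **Who can see it?** Section 8.5 does not restrict these records to unblinded staff. Sections 14.2 and 16.1 open medical records and source documents to monitors, who are not on the section 8.7 list.

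4. **Is the label masked elsewhere?** Appendix E has unblinded or delegated staff cover the vial label, bag the vial and mask the syringes. It does not mention tracking labels. The vial steps follow thawing, so they do not protect the label at receipt.

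5. **When would disclosure begin?** The first dose is on Day 1. Table 1 schedules UENS and NIS-LL after baseline on Days 29, 93, 186 and 365. A chart label filed at the first dose would precede all four.

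6. **Scale.** Inputs: 8 subjects per arm (section 10.3) and 3 administrations each (section 8.2), taking one unit per administration because the 4.5 mL unit in section 8.1 equals the 4.5 mL injected.
   - Active: 16 × 3 = 48 units, inside the rule on the literal reading.
   - Placebo: 8 × 3 = 24 units, outside it.
   - Total: 48 + 24 = 72 units.

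7. **What a vial label could show.** Both strengths are in 4.5 mL, so the concentrations are 3/4.5 ≈ 0.67 and 30/4.5 ≈ 6.7 million cells per mL, a 10-fold difference. Section 8.4 ties the concentration entry to active cells. Anyone who reads an uncovered vial label could distinguish active from placebo, and the two doses.

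**The case against.** The strongest reply is that the text does not force unblinding. Several stronger conclusions that a reader might draw are not supported:

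- **That chart filing is required.** It is not. The sentence allows another record, and a site that uses a pharmacy file complies and protects the blind.
- **That a chart without a label identifies placebo, so all 24 subjects can be classified.** This needs every site to file in the chart, placebo units to have no equivalent label, and the label to be legible to blinded staff. None of these is established. The protocol also uses PDA-002 loosely for blinded product: in the stopping rules of section 12.1.2, in the name of the receipt record, and in the title of the Appendix E thawing instructions. Labels on every unit would fit that usage. Section 8.3 also refers handling to a pharmacy manual that is not part of these documents.
- **That the tracking label reveals dose.** Its content is not given. The dose difference in the working concerns vial labels only.
- **That the investigator must read vial labels.** A designee may do the inspection, and the unblinded pharmacist can be that designee. Product stays in the shipper until use.
- **That the primary endpoint is compromised.** Section 6.4 has a pathologist count ENFD, and nothing shows that this person sees the chart. For NTSS-6, Norfolk QOL-DN and PGICN, which rest on subject report, no route is described by which subjects would see a chart label.

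These limits stand. They reduce the point from certain to possible unblinding. They do not supply a safeguard: an ambiguous scope and an optional location still leave a compliant site free to expose allocation.

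**Conclusion.** The concern holds as a conflict between a written rule and the blind. Section 8.5 permits, without requiring, a filing practice that marks active recipients in records open to blinded examiners and monitors. It also permits a blinded investigator to inspect shipments whose active vials state cell concentration. Sections 8.3 and 8.7 require those people to stay blinded, and no provision reconciles the two.

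The label route rests on two assumptions: that PDA-002 in the tracking sentence has its section 8.1 meaning, and that at least one site uses the chart. On the first, 48 of 72 planned units are covered. How many subjects would actually be revealed cannot be estimated from the documents. The receipt route assumes only that the investigator inspects personally and sees the vial labels.

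The clearest exposure is UENS, NIS-LL, and adverse event severity and causality. The point should not be cited as evidence of bias in ENFD.

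**What to change.** - **Tracking labels.** In section 8.5, direct that during the study they be filed only in a restricted pharmacy file held by the unblinded pharmacist or designee, which the present wording already allows. Alternatively, or in addition, supply identical coded labels for all arms, including placebo.
- **Shipments.** Name the unblinded pharmacist or designee as the person who receives and inspects shipments, completes the receipt record and does accountability.
- **Access.** Keep any record that reveals treatment out of the files open to blinded site staff and blinded monitors. Reconcile this with the sponsor-access wording in section 8.5 by routing access through people already listed as unblinded in section 8.7.

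The cost is protocol and pharmacy-manual wording, plus a placebo label print if coded labels are chosen. The site role already exists. There are two small downsides: during the study, tracing between donor and recipient runs through the pharmacy file rather than the chart, and review of those records must be separated from blinded monitoring, because section 16.1 now has one sponsor representative review everything.
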